6.2.1	Baseline Data	14
6.2.2	Efficacy Analysis	14
6.2.3	Safety Analysis	15
6.3	SAMPLE SIZE AND POWER	15
7	SAFETY MANAGEMENT	16
7.1	CLINICAL ADVERSE EVENTS	16
7.2	ADVERSE EVENT REPORTING	16
8	STUDY ADMINISTRATION	16
8.1	TREATMENT ASSIGNMENT METHODS.....	16
8.1.1	Randomization	16
8.1.2	Blinding	17
8.2	DATA COLLECTION AND MANAGEMENT	17
8.3	CONFIDENTIALITY	17
8.4	REGULATORY AND ETHICAL CONSIDERATIONS	17
8.4.1	Data and Safety Monitoring Plan	17
8.4.2	Risk Assessment	18
8.4.3	Potential Benefits of Trial Participation	18
8.4.4	Risk-Benefit Assessment	19
8.5	RECRUITMENT STRATEGY	19
8.6	INFORMED CONSENT/ASSENT AND HIPAA AUTHORIZATION	19
8.7	PAYMENT TO SUBJECTS/FAMILIES.....	20
8.7.1	Reimbursement for travel, parking and meals	20
8.7.2	Payments to parent for time and inconvenience (i.e. compensation)	20
8.7.3	Payments to subject for time, effort and inconvenience (i.e. compensation)	20
8.7.4	Gifts	20
9	PUBLICATION	20
10	REFERENCES	21

ABBREVIATIONS AND DEFINITIONS OF TERMS

TD: Typically developing

CP: Cerebral Palsy

GMFM: Gross Motor Function Measure

BSID-III: Bayley Scales of Infant and Toddler Development, version III

PT: Physical therapy

ABSTRACT

Context: Cerebral palsy (CP) is the most common cause of physical disability in children. There is a window of opportunity to reduce the degree of lifelong disability by maximizing motor potential during the critical early years of development.

[figure not shown]
Objectives: 1) To determine the optimal treatment duration of a novel early mobility training program (dynamic supported mobility, DSM) between 6 to 24 weeks of treatment; and 2) To evaluate the clinical futility of this intervention compared to current rehabilitation practice.

Study Design: Exploratory clinical trial

Setting/Participants: Sixty participants with, or with suspected, CP between the ages of 1-3 years will be enrolled. All testing procedures and interventions will occur in the Center for Rehabilitation at CHOP on an outpatient basis.

Study Interventions and Measures: Study participants will be randomly assigned to receive either dynamic supported mobility (DSM, experimental) treatment or intensity-matched conventional treatment. Repeated assessments of gross motor function will be performed during the treatment phase and at three follow-up points over one year after treatment to track the developmental trajectory of participants' motor function. Gross motor outcomes of DSM treatment will be compared to published percentile scores of motor function development in CP to determine if the trajectory of predicted motor development is altered, and to outcomes of intensity-matched conventional treatment.

TABLE 1: SCHEDULE OF STUDY PROCEDURES

FIGURE 1: STUDY DIAGRAM

1 BACKGROUND INFORMATION AND RATIONALE

1.1 Introduction

As the most common cause of physical disability in children, CP is a disorder “...of the development of movement and posture... attributed to non-progressive disturbances that occurred in the developing fetal or infant brain.”¹ Given the age at onset and the near-typical lifespan,² those living with cerebral palsy (CP) experience one of the highest number of disability-years among all disabling conditions. CP is the most common cause of motor disability in children³ with a prevalence that has remained stable over recent decades at more than 3 per 1000 births or 10,000 babies per year in the United States despite advances in pre- and perinatal care.^{4,5} An estimated 15 million people currently live with CP worldwide. The degree of life participation restriction in those with CP is predicted by the degree of motor disability, which varies widely from limitations in balance and coordination to full dependence on others for care.⁶ This relationship between severity of motor disability and participation restriction has been reported in infancy,⁷ childhood,^{8,9} and adolescence and young adulthood.¹⁰ Independent of cognitive impairment, the severity of physical disability in childhood is a predictor of later romantic relationships¹¹ and independent living in the early 30s.¹²

The best opportunity to maximize lifelong independence is early in motor development when the differences in motor skill between functional levels are relatively small and there is the most potential for neuroplastic change. Gross motor function plateaus by 4-7 years of age¹³ after which motor ability is relatively fixed with large skill gaps between levels. In fact, the Gross Motor Function Classification System (GMFCS)⁶ of motor severity remains relatively stable throughout childhood and adulthood,^{14,15} regardless of treatment. *However, the early years of life are an exception* with less stability in GMFCS classifications before the age of 2 years.¹⁶ There is also growing evidence of a critical period of neuroplasticity for motor control centers in the brain. Similar to the development of sensory systems, recent work has confirmed that plasticity in the motor system is both activity-dependent, and more robust in early as compared to later years.^{17,18} Moreover, maladaptive changes that occur after central nervous injury are difficult to reverse once established.¹⁹ These observations suggest that there is a window of opportunity for interventions applied *prior* to nearing the developmental peak to improve the trajectory of motor development and reduce lifelong physical disability.

How best to optimize motor ability during this narrow window remains unknown. Current practice does not reflect key learning principles of typical motor development. Typical toddler movement is characterized by a high degree of motor exploration, error and movement variability, which are critical factors in the refinement of motor control. Infants and toddlers with CP often cannot create these experiences on their own, losing natural opportunities to learn more coordinated movements and establish the associated neural pathways that control skilled movement. In contrast to their typically-developing peers, young children with CP instead repeatedly practice poorly-controlled motor patterns. Our work will investigate a promising novel treatment designed to allow infants and toddlers with CP to create for themselves motor learning experiences more similar to their typically developing peers. This contribution will be significant because the treatment may have the potential to improve the trajectory of motor development and reduce lifelong physical disability in individuals with CP. The work will increase our understanding of how best to

optimize the potential of the developing brain to recover after neuromotor injury. As such, the proposed work will also inform the early treatment practices for other developmental disorders, such as early brain injury, Down Syndrome, and various neurogenetic disorders.

1.2 Name and Description of Investigational Intervention

Dynamic Supported Mobility (DSM) - The experimental therapy group will receive dynamic weight support (using the ZeroG Gait and Balance training system, Aretech LLC, Ashburn, VA) during all therapy time, and the environment will be arranged to encourage active motor exploration by the child, in order to promote the motor variability, challenge, and error experiences that characterize the typical development of upright motor skills and walking. Activities will be graded in difficulty to the child's ability and will include: moving between the floor and standing, walking, squatting to reach the floor, climbing/walking up and down steps and inclines, and other typical toddler movements, somewhat similar to a play gym for toddlers. The floor area within 3 feet below either side of the overhead track for a distance of approximately 20 feet (approximately 120 ft² total) will be defined with colorful thin rubber interlocking mats and arranged with pediatric toys and activities, tailored to the child's interests and to encourage motor skills just beyond his/her current ability level. The dynamic support system continuously provides a constant amount of weight assistance (as determined by the therapist) by controlling the length of the cable joining the harness and track and by moving along the overhead track as the user moves about the space (i.e. cable lengthens if child moves to the floor and shortens if child climbs up steps, with no lag time). The user's movements are not restricted at all within this space. This arrangement works well to keep children within the limits of the overhead track and provide ample opportunity and space for motor play and exploration. Initial amount of weight assistance will be determined during the first therapy session by the level that allows walking and squatting to reach the floor with the least amount of assistance from the therapist. Weight assistance will be gradually reduced during the treatment phase as postural control and coordination improve. The therapist will minimally assist the child as needed to perform the movements he/she initiates.

1.3 Relevant Literature and Data

The proposed intervention has been systematically developed and pilot-tested consistent with a stage model for behavioral therapies.²⁰ The treatment was designed to incorporate overlapping principles of neurorehabilitation and infant motor learning in a context that promotes upright mobility skill and postural control development.

Treatment development.

Principles of neurorehabilitation. Despite increasing evidence of early critical periods for neuroplasticity,^{17,18} there remains little application to individuals with CP. Treatments addressing secondary musculoskeletal impairments such as muscle and bone abnormalities that develop in response to poor motor control remain the most common treatment approaches.²¹ These interventions are important to manage the course of CP, but do not address the primary impairment of poor neural control of movement.¹ The most effective rehabilitation programs include intensive, early, and challenging motor practice,²²

²⁴ and these principles are supported by training-dependent plasticity in cortical structures.²⁵⁻²⁷ *Variability* in movement patterns during rehabilitation further enhances motor outcomes^{28,29} and reflects complex motor skill.³⁰ *Salience* is the meaningfulness of the training to the patient which promotes active engagement and facilitates neuroplasticity.^{31,32} Finally, the critical role of *error* in motor learning and rehabilitation has been increasingly recognized,^{33,34} with diminished long-term gains when error is eliminated from practice.³⁵

Two methods of interpreting the preliminary data support prospective comparison of the functional outcomes of DSM treatment to conventional rehabilitation practice. First, the four participants who would meet the proposed selection criteria were receiving other rehabilitation services throughout the study and demonstrated rates of motor development during the DSM treatment phase that were 3.8 to 15.1 times their respective rates of motor development during the baseline phase (Table 1). This suggests that the DSM treatment significantly accelerated their individual rates of motor skill attainment with conventional rehabilitation services. However, motor development is not always linear,⁴⁷ so this approach is not sufficient to determine the treatment's futility compared to other treatments. Second, the same four participants all demonstrated net changes (ranging from 2.4-9.7, Figure 2) after only six weeks of treatment that exceeded the corresponding minimal clinically important difference values for treatments that have a large effect size (1.5 for GMFCS level II and 1.3 for level III).⁴⁵ However, caution should be taken as these minimal clinically important difference values were determined from a sample of children aged 4-18 years, and while unknown, it is possible that the minimal clinically important difference values would be larger earlier in development. Although promising, prospective comparison to intensity-matched current rehabilitation intervention is needed to confirm the potential advantages of DSM treatment prior to progression to a larger efficacy trial. These data support the foundation of Hypothesis 2.2 that children who receive DSM treatment will demonstrate greater gains in gross motor function than participants who receive equal amounts of CONV treatment.

Other Relevant Literature

Determining the optimal dose of pediatric rehabilitation services for children with CP and other developmental disabilities has been identified as a national priority.⁴⁸ Yet, the majority of research in the field has not explored dose-response outcomes for various interventions. The convenient, rather than scientifically-grounded, dosing of neuromotor rehabilitation historically offered during clinical trials often limits the validity and comprehensiveness of the research findings. Investigation of treatment response over a duration long enough to reach an anticipated behavioral plateau in the early stages of scientific inquiry more adequately prepares an experimental rehabilitation treatment for Phase III efficacy evaluation.⁴⁹

Both the National Institute of Neurological Disorders and Stroke (www.ninds.nih.gov) and leaders in neurology⁵⁰ and neurorehabilitation⁵¹ suggest that early clinical trials are the appropriate stage at which to evaluate the futility of a new treatment compared to another treatment or standard of care. These data are critical in determining if and how the science should progress in a definitive Phase III trial. Dobkin further emphasizes that while “a nonactive placebo may be the only therapy in a drug trial if no standard drug therapy exists, comparing a specific rehabilitation treatment to nothing is no longer acceptable.” (2009) The intensity of treatment (minutes per week) in the proposed study will approximate the average amount of physical therapy received by young children with CP in the United States. The average amount of physical therapy is 82 (SD 60) minutes per week in the United States, and 90 (SD 60) minutes per week in the Philadelphia metropolitan area.⁵² The 90 minutes per week of either treatment in the proposed study reflects this current intervention practice. However, the wide variability in the standard

amount of services means that not all children would receive this intensity outside of the research study. This variability in current practice is a common issue in identifying “standard of care” in rehabilitation trials. However, it has been determined in gold-standard trials that matching the treatment intensity of the experimental group is the most important component of the “control” group,^{24,53} and our approach reflects this standard.

1.4 Compliance Statement

This study will be conducted in full accordance all applicable Children’s Hospital of Philadelphia Research Policies and Procedures, all applicable Federal and state laws and regulations, and the Good Clinical Practice: Consolidated Guideline approved by the International Conference on Harmonisation (ICH). All episodes of noncompliance will be documented. The investigators will perform the study in accordance with this protocol, will obtain consent and assent, and will report unanticipated problems involving risks to subjects or others in accordance with The Children’s Hospital of Philadelphia IRB Policies and Procedures and all federal requirements. Collection, recording, and reporting of data will be accurate and will ensure the privacy, health, and welfare of research subjects during and after the study.

2 STUDY OBJECTIVES

2.1 Primary Objectives (or Aims)

Aim 1. To determine the optimal treatment duration of dynamic supported mobility (DSM) treatment in infants and toddlers with cerebral palsy, between 6 to 24 weeks of treatment.

Hypothesis 1.1. Gross motor ability (measured by the GMFM-66) will exceed individual predicted values in infants and toddlers with cerebral palsy after 12, 18, and 24 weeks of DSM treatment, and gains will be maintained at 3, 6 and 12 month follow-up points.

Hypothesis 1.2. Gross motor function gains will be positively related to the amount of motor error, variability and engagement experienced during DSM treatment.

Aim 2. To determine the futility of dynamic supported mobility compared to conventional rehabilitation in infants and toddlers with cerebral palsy.

Hypothesis 2.1. The frequency of adverse events among participants who receive DSM treatment and those who receive conventional (CONV) treatment will not differ by greater than 10 percent.

Hypothesis 2.2. Participants who receive DSM treatment will demonstrate significantly greater improvements in gross motor ability (measured by the GMFM-66) than participants who receive equal amounts of CONV treatment, and these differences will be maintained at each follow-up point.

2.2 Secondary Objective (or Aim)

The secondary objective is to:

- Compare physical activity at home, postural control, engagement in daily life, caregiver satisfaction and cognition in the dynamic supported mobility (DSM) therapy group to the conventional (CONV) therapy group.

3 INVESTIGATIONAL PLAN

3.1 General Schema of Study Design

The proposed study is a single-blind, randomized exploratory clinical trial with repeated assessments during a 24-week treatment phase and at three follow-up points over 12 months after treatment to track the developmental trajectory of participants' motor function. Gross motor ability will be compared to published percentile scores of motor function development in CP to determine if the trajectory of predicted motor development is altered, and to outcomes of intensity-matched conventional treatment to determine if continued Phase III investigation is warranted.

3.1.1 Screening Phase

Candidate screening will be conducted by the primary research therapist using the protocol inclusion and exclusion criteria. The parent or legal guardian must provide written informed consent prior to the start of any study activities. Written assents of minors will not be obtained due to the age of the participants.

3.1.2 Study Treatment Phase (start of the study intervention)

Children will be able to continue their outside therapies, if their families' choose to do so. Whether they reduce or continue their pre-enrollment therapy schedule, families will be asked to maintain the schedule of outside physical therapy constant throughout the treatment phase. It is anticipated that most children will be receiving early intervention therapy services in the home. Other medical care will be documented but not restricted. If parents sign CHOP's standard HIPAA authorization, we will request copies of outside therapy notes to assist with documentation of co-occurring treatments. Treatment will start within one week of Assessment 1 and will be delivered by the primary or secondary research physical therapist, both of whom will be trained using the study manual to provide each type of treatment. We will follow intent to treat procedures such that no child will be withdrawn from the study for failing to adhere to the therapy schedule. A training log will be maintained for each session. One session per week will be videotaped (if separate consent is provided) for quality control to ensure that activities between the treatments remain different and are consistent with the distinguishing characteristics.

After enrollment and the initial assessment, participants will be randomized to receive either DSM or conventional (CONV) treatment, using a randomization scheme to ensure that motor ability does not differ at baseline. Participants will also be randomly assigned to either the primary or secondary research therapist who will each provide both

types of treatments, to minimize any differences related to individual therapist. Treatment in both groups will occur at an intensity of 3 times per week for 30 minutes.

DSM treatment. Children will receive dynamic weight support (ZeroG®, Aretech LLC, Ashburn, VA) during all DSM treatment time. The environment will be arranged to encourage active motor exploration, somewhat similar to a play gym for toddlers, to promote the motor variability, engagement, and error experiences that characterize the typical development of upright motor skills and walking. The floor area within 3 feet below either side of the overhead track for a distance of 20 feet (approximately 120 ft² total) will be defined with colorful thin rubber interlocking mats and arranged with pediatric toys and activities, tailored to the child's interests and to encourage motor skills just beyond his/her current ability. This arrangement worked well in pilot work to keep children within the limits of the overhead track and provide ample opportunity and space for motor play and exploration. Initial amount of weight assistance will be determined by the level that allows walking and squatting to reach the floor with the least amount of assistance from the therapist, up to a maximum of 40% of the child's weight. Greater than 40% weight support produces significant alterations in normal walking biomechanics in healthy adults (unpublished data, communication with system inventor, [name], PhD). Amount of weight assistance will be re-assessed at the start of each session, and will be gradually reduced as postural control and coordination improve to the minimum amount that allows walking and squatting to reach the floor with the least amount of assistance from the therapist. The therapist will minimally assist the child as needed to perform the movements he/she initiates.

CONV treatment. The conventional treatment group will receive traditional, therapist-directed pediatric physical therapy. Therapy will focus on early gait training strategies and encouragement of "normal" movement patterns for walking and other age-appropriate movements, with manual guidance or correction of atypical movements from the therapist. This group may use assistive devices, orthoses, and may receive static body weight support for gait training. Therapy activities will be performed in blocks of practice, with the specific activities and level of therapist assistance tailored to each child. Examples include: using a posterior rolling walker with ankle foot orthoses (braces), physically guided practice of standing from the floor through half kneeling, manual correction of side steps while cruising at a bench, and repeated sit to stand practice from a small chair. The distinguishing characteristics of each treatment are listed in Table 4.

3.1.3 Follow-up Phase

The treatment phase will end after 24 weeks of treatment. Three follow-up assessments will occur at 3, 6 and 12 months after treatment ends.

3.2 Allocation to Treatment Groups and Blinding

After the initial GMFM-66 score from Assessment 1 is obtained, participants will be randomized to either the CONV or DSM treatment, using a randomization scheme to stratify by baseline motor ability. This will ensure that the groups do not differ in motor ability at baseline. Participants will also be randomly assigned to either the primary or secondary research therapist who will each provide both types of treatments, to minimize any differences related to individual therapist. A blinded assessor will collect all outcomes

measures. Blinding of participants to treatment group is not feasible with the proposed interventions.

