6 STATISTICAL CONSIDERATIONS

6.1 Primary Endpoint

The primary endpoint will be the change in GMFM (Gross Motor Function Measure) from baseline to each post-treatment assessment session.

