To address Aim 2, Hypothesis 2.2 (*Participants who receive DSM treatment will demonstrate greater improvements than participants who receive CONV treatment, and the differences will be maintained at follow-up*) will be analyzed by comparing GMFM-66 outcomes between participants receiving DSM treatment and those receiving CONV treatment. Baseline characteristics in each group will be compared using two-sample tests, including t-tests, the Mann-Whitney test, and chi-square tests, as appropriate for the respective type of data. We will then use a univariate approach for comparing the two treatments using analyses of variance and covariance (ANCOVA). Measurements at 6, 12, 18 and 24 weeks, as well as at both follow-up points after treatment will be individually compared between the two treatment conditions using baseline score, cognition and caregiver self-efficacy as covariates. We will also use a multivariate approach using linear mixed effects model⁵⁹ or the Generalized Estimating Equation (GEE).⁶⁰ The advantage of using the mixed effects model or the GEE approach is that they will not drop subjects from the analysis due to not having measurement at any of the post-treatment time points. Also, such analyses will allow us to examine the between subjects effects which represent a factor with two levels (treatment conditions) and within subjects effects which represent time effects (pre and post measurements) and a time by condition interaction. The random effect model will be implemented utilizing SAS Proc Mixed and the GEE will be implemented by SAS Proc Genmod. (SAS/STAT User's Guide, 2004, Version 9. Cary, NC: SAS Institute, Inc). Cognition and caregiver self-efficacy will be included as covariates in these analyses. Two-sided p values of less than 0.05 will be considered statistically significant. Similar procedures will be used for the analysis of secondary outcomes, with appropriate tests for parametric (postural control, physical activity) and non-parametric measures (caregiver satisfaction, Child Engagement in Daily Life).

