8 STUDY ADMINISTRATION

8.1 Treatment Assignment Methods

8.1.1 Randomization

After the initial GMFM-66 score from Assessment 1 is obtained, participants will be randomized to either the CONV or DSM treatment, using a randomization scheme to stratify by baseline motor ability. This will ensure that the groups do not differ in motor ability at baseline. Participants will also be randomly assigned to either the primary or secondary research therapist who will each provide both types of treatments, to minimize any differences related to individual therapist. A blinded assessor will collect all outcomes measures. Blinding of participants to treatment group is not feasible with the proposed interventions.

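### The mixed model/GEE leaves the condition effect at baseline free instead of adjusting for baseline GMFM-66, so its confidence interval is somewhat wider than it needs to be

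*Combined protocol and SAP*

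**What the plan says.** Section 6.1 defines the endpoint: "The primary endpoint will be the change in GMFM (Gross Motor Function Measure) from baseline to each post-treatment assessment session". Section 6.2.2 then gives two between-arm analyses of GMFM-66.

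- **Visit-wise ANCOVA.** Measurements are "individually compared between the two treatment conditions using baseline score, cognition and caregiver self-efficacy as covariates".
- **Repeated-measures model.** "We will also use a multivariate approach using linear mixed effects model", with GEE as the alternative. Its terms are condition and "within subjects effects which represent time effects (pre and post measurements) and a time by condition interaction". On adjustment it says: "Cognition and caregiver self-efficacy will be included as covariates in these analyses".

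The baseline score is in the first covariate list and not in the second. In the repeated-measures model it enters as the pre-treatment response, and nothing says that the two arms share a baseline mean. The stated advantage of this model is that children with missing visits stay in. Neither analysis is named as primary.

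On allocation, section 8.1.1 describes "using a randomization scheme to stratify by baseline motor ability", without giving cut-points, number of strata or block size. Sections 3.2 and 8.1.1 both say of this scheme: "This will ensure that the groups do not differ in motor ability at baseline".

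**The concern.** Two analyses of the same outcome treat baseline differently. The ANCOVA uses the baseline score to reduce residual variance. The repeated-measures model, with a free condition effect at baseline, compares changes from baseline instead. When the correlation between baseline and later score is below 1, the change comparison has the larger variance.

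This matters because section 6.3 sizes the trial on confidence-interval width and targets no power. Interval width is therefore the design criterion, and the model chosen to retain the most children does not make full use of a measurement already taken. The assurance of baseline balance may also lead a reader to think that adjustment is unnecessary.

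**Working it through.** **Inputs.** Section 6.3: 17 per arm, SD 9, half-width 6 for a two-sided 95% interval, 21 randomised per arm, 20% attrition anticipated. The correlation rho between the baseline and a later GMFM-66 score is not given, so 0.5 to 0.9 is assumed. Section 6.3 does not say whether SD 9 refers to change or to the score at one visit; both are shown.

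**The plan's figure.** 1.96 × 9 × sqrt(2/17) = 6.05, which reproduces the stated 6.

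**Formulae.** With n per arm, complete data and equal variance s² at both visits:

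- free condition effect at baseline, time-by-condition contrast: variance (2/n) × 2s²(1 − rho), the same as for a change score;
- common baseline mean, or baseline as covariate: variance (2/n) × s²(1 − rho²);
- ratio of the second to the first: (1 + rho)/2.

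Generalised least squares with one post-treatment visit confirms this for s = 9 and n = 17. The free model has SE 3.09, 2.39, 1.95 and 1.38 at rho 0.5, 0.7, 0.8 and 0.9. The common-baseline model has 2.67, 2.20, 1.85 and 1.35. Cognition and self-efficacy, if entered as time-constant main effects, leave the complete-data contrast unchanged.

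**Effect on the 95% half-width, 17 per arm.**

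| rho | (1 + rho)/2 | narrowing | if SD 9 is of change | if SD 9 is of one score |
|---|---|---|---|---|
| 0.5 | 0.75 | 13.4% | 6.05 to 5.24 | 6.05 to 5.24 |
| 0.7 | 0.85 | 7.8% | 6.05 to 5.58 | 4.69 to 4.32 |
| 0.8 | 0.90 | 5.1% | 6.05 to 5.74 | 3.83 to 3.63 |
| 0.9 | 0.95 | 2.5% | 6.05 to 5.90 | 2.71 to 2.64 |

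Narrowing is 1 − sqrt((1 + rho)/2). In sample-size terms, 17/0.75, 17/0.85 and 17/0.95 give about 23, 20 and 18 per arm without adjustment for the precision of 17 with it (rho 0.5, 0.7, 0.9).

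**With stratification.** A simulation used 6,000 trials per setting, 34 children, SD 9 at both visits and complete data at one post-treatment visit. Two strata split at the mean and blocks of 4 were assumed. Stratification cut the SD of the baseline difference from about 3.1 to about 1.9 points. A gap above 3 points still arose in about 12% of trials, against about 33% without stratification.

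| rho | change: true SE | change: reported SE | ANCOVA: true SE | ANCOVA: reported SE |
|---|---|---|---|---|
| 0.5 | 2.86 | 3.07 | 2.73 | 2.67 |
| 0.8 | 1.88 | 1.94 | 1.85 | 1.84 |

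The true SEs are close. The change contrast reports an SE above its true value, so most of the loss appears as an over-wide interval.

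**Effect of a chance gap.** A baseline gap d shifts the change contrast by about (1 − rho)d. For d = 3 this is 1.5, 0.9 or 0.3 points at rho 0.5, 0.7 or 0.9. Section 6.3 predicts a difference of 10.6 − 1.8 = 8.8.

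**The case against.** The strongest reply is that baseline is already dealt with: the ANCOVA adjusts for it, the repeated-measures model contains it as a response, and the interaction allows for a baseline difference. That is right as far as it goes. A reader might infer that the repeated-measures model ignores baseline altogether; section 6.2.2 does not support that. What remains is that a free baseline difference is the less efficient way to use it.

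Three other inferences also fail.

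- *The change contrast is biased.* Under randomisation it is unbiased. The shift of (1 − rho)d is conditional on a chance gap, and stratification makes large gaps less likely.
- *Leaving the stratum out of the models is itself a fault.* Once continuous baseline is in the model, adding the stratum gained nothing in the simulation (SE 1.88 with it, 1.85 without, at rho 0.8).
- *The mixed model is always less precise than the ANCOVA.* The complete-data ratio ignores dropout. With 21 randomised and 17 completing per arm, and dropouts leaving after week 6, 12 or 18 under compound-symmetry or autoregressive correlation (both assumed), the free mixed model's SE relative to a 17-per-arm ANCOVA was 7 to 12% larger at rho 0.5 and 1 to 5% larger at 0.7. It ran from 3% larger to 2% smaller at 0.8, and from equal to 5% smaller at 0.9. Retaining children can offset the loss, but a common baseline mean would keep both advantages.

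It is also fair that an over-wide interval errs on the cautious side and that no power is targeted. Both points make this a modest matter without removing it.

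**Conclusion.** The point holds as a modest, nearly free gain in precision. As written, the mixed model/GEE contrast is essentially a change-score difference. Baseline adjustment would narrow its reported 95% interval by about 13%, 8% or 3% at correlations of 0.5, 0.7 or 0.9. Those sizes rest on an assumed correlation, equal variances and complete data, and on reading the text as leaving the condition effect free at baseline. The simulation also rests on assumed strata and block size. The documents do not support a claim of bias, of baseline being left out entirely, or of harm from omitting the stratum. Separately, the statement that stratification guarantees equal groups is too strong for a trial of this size.

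**What to change.** In section 6.2.2, state how baseline enters the repeated-measures model. Either option works:

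1. **Preferred.** Keep pre- and post-treatment scores as responses and constrain the baseline mean to be equal across arms. Every randomised child with a baseline stays in.
2. **Alternative.** Model the post-baseline visits only, with baseline GMFM-66 and baseline-by-visit as covariates. Children with only a baseline drop out, and a few degrees of freedom are used.

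If GEE is kept, adjust for baseline in the same way. In sections 3.2 and 8.1.1, say that stratification limits baseline differences between the groups, in place of the guarantee.

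The cost is a change of wording. The baseline score is already collected and already used in the ANCOVA, so no extra visit, measurement or child is needed.
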